7.1 Adverse events

An adverse event (AE) is any untoward medical occurrence (i.e., any unfavorable and unintended sign [including abnormal laboratory findings], symptom or disease) in a subject or clinical investigation subject *after providing written informed consent* for participation in the study. Therefore, an AE may or may not be temporally or causally associated with the use of a medicinal (investigational) product.

The occurrence of adverse events should be sought by non-directive questioning of the patient at each visit during the study. Adverse events also may be detected when they are volunteered by the patient during or between visits or through physical examination, laboratory test, or other assessments.

Abnormal laboratory values or test results constitute adverse events only if they fulfill at least one of the following criteria:

- they induce clinical signs or symptoms,
- they are considered clinically significant,
- they require therapy.

Adverse events should be recorded in the Adverse Events CRF under the signs, symptoms or diagnosis associated with them, accompanied by the following information:

- the severity grade
 - mild: usually transient in nature and generally not interfering with normal activities
 - moderate: sufficiently discomforting to interfere with normal activities
 - severe: prevents normal activities
- its relationship to the study medication
- study treatment (no/yes), or
- investigational treatment (no/yes), or
- the other study treatment (non-investigational) (no/yes), or
- both or indistinguishable,
- its duration (start and end dates) or if the event is ongoing an outcome of not recovered/not resolved should be reported

- whether it constitutes a serious adverse event (SAE - See section 7.2 for definition) action taken regarding canakinumab treatment.

All adverse events should be treated appropriately. Treatment may include one or more of the following:

- no action taken (i.e. further observation only)
- study treatment dosage adjusted/temporarily interrupted
- study treatment permanently discontinued due to this adverse event
- concomitant medication given
- non-drug therapy given
- patient hospitalized/patient's hospitalization prolonged
- its outcome (not recovered/not resolved; recovered/resolved; recovering/resolving, recovered/resolved with sequelae; fatal; or unknown)

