7.2 Serious adverse event (SAE)

7.2.1 Definition of a SAE

A SAE is defined as any adverse event (appearance of (or worsening of any pre-existing) undesirable sign(s), symptom(s) or medical conditions(s) which meets any one of the following criteria:

- is fatal or life-threatening
- results in persistent or significant disability/incapacity
- constitutes a congenital anomaly/birth defect
- requires inpatient hospitalization or prolongation of existing hospitalization, unless hospitalization is for:
 - routine treatment or monitoring of the studied indication, not associated with any deterioration in condition (specify what this includes)
 - elective or pre-planned treatment for a pre-existing condition that is unrelated to the indication under study and has not worsened since signing the informed consent
 - treatment on an emergency outpatient basis for an event not fulfilling any of the definitions of a SAE given above and not resulting in hospital admission
- social reasons and respite care in the absence of any deterioration in the patient's
- general condition
- is medically significant, i.e. defined as an event that jeopardizes the patient or may require medical or surgical intervention.

Life-threatening in the context of a SAE refers to a reaction in which the patient was at risk of death at the time of the reaction; it does not refer to a reaction that hypothetically might have caused death if more severe (see ICH-E2D Guideline available at:

http://www.ich.org/fileadmin/Public_Web_Site/ICH_Products/Guidelines/Efficacy/E2D/Step4/E2D_Guideline.pdf).

All malignant neoplasms will be assessed as serious under “medically significant” if other seriousness criteria are not met.

Any suspected transmission via a medicinal product of an infectious agent is also considered a serious adverse reaction.

Medical and scientific judgment should be exercised in deciding whether other situations should be considered serious reactions, such as important medical events that might not be immediately life threatening or result in death or hospitalization but might jeopardize the patient or might require intervention to prevent one of the other outcomes listed above. Examples of such events are intensive treatment in an emergency room or at home for allergic bronchospasm, blood dyscrasias or convulsions that do not result in hospitalization or development of dependency or abuse (see ICH-E2D Guideline available at:

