9.4 Analysis of variables

9.4.1 Variables

a. Efficacy variables

There is no efficacy assessment in this study

b. Safety variables

Adverse events will be coded using the MedDRA dictionary that provides the primary system organ class and preferred term information. Adverse events will be presented in two parts:

- Adverse events (including infections)
- Infectious adverse events

Adverse events will be summarized for each disease by presenting the number and percentage of patients having any adverse event, having any adverse event in each primary system organ class and having each individual adverse event based on the preferred term. All other information collected (e.g. severity, relationship to study drug, or microorganism for infectious adverse events) will be tabulated and listed as appropriate.

Deaths, serious adverse events, and adverse events leading to discontinuation of study drug will be summarized by primary system organ class and preferred term and listed.

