2.8.1 Adverse events (AEs)

Adverse events starting on or after the time of the first dose of study drug but not later than 7 days (30 days in the case of a SAE) after the date of last dose of study drug taken or those AE present at baseline with increased severity will be classified as a TEAE and will be included in all summaries. AEs which started and ended prior to baseline and AEs which started prior to baseline but whose severity does not change post baseline will not be included in treatment emergent adverse event. In addition, all the treatment emergent AEs will also be listed.

The by-patient listing includes, SOC/PT/Verbatim term, start date, end date, the severity of an AE, Seriousness, whether or not an AE is related to study drug, and whether or not it is a serious AE, action taken with study drug, outcome, duration, discontinue from study. Duration will be calculated as end date – start date +1 and for ongoing last visit date – start date +1.

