2.8.1.1 Adverse events of special interest / grouping of AEs

AEs by primary system organ class and preferred term

The number and percentage of patients who reported treatment emergent adverse events will be summarized for each primary system organ class and preferred term. Primary system organ classes will be sorted alphabetically and, within each primary system organ class, the preferred terms will be sorted in descending order of frequency.

If a patient reported more than one adverse event with the same preferred term, the adverse event will be counted only once at the preferred term level. If a patient reported more than one adverse event within the same primary system organ class, the patient will be counted only once at the system organ class level.

Treatment emergent adverse events will be presented in two parts:

- Adverse events (including infections)
- Infectious adverse events

AEs by severity

All treatment emergent adverse events will be summarized by maximum severity for each primary system organ class and preferred term. If a patient reports more than one adverse event within the same primary system organ class, only one adverse event will be counted for that patient at the highest severity level in the total row for each primary system organ class. If a patient reported more than one adverse event with the same preferred term, the highest (maximum) severity will be presented.

AEs suspected to be related to study drug

The treatment emergent adverse events suspected to be related to the study drug (according to the investigators) will be summarized by primary system organ class and preferred term. Relationship to study drug is considered as suspected for those events where "Relationship to study drug" is answered by the investigator as "Suspected".

AEs leading to permanent study drug discontinuation

Treatment emergent adverse events leading to permanent study drug discontinuation will be summarized by primary system organ class and preferred term.

Serious Adverse Event (SAE)

Number and percentage of patients with serious adverse events, regardless of study drug relationship, will be presented by primary system organ class and preferred term.

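### The SAP limits the discontinuation table and the AE listing to treatment-emergent events, so a baseline AE that stops treatment at an unchanged grade is missing from both, although Protocol 9.4.1 sets no such limit

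*SAP*

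**What the plan says.** SAP 2.8.1 gives an event present at baseline one route to treatment-emergent status: "those AE present at baseline with increased severity will be classified as a TEAE and will be included in all summaries". It then closes the other routes: "AEs which started prior to baseline but whose severity does not change post baseline will not be included in treatment emergent adverse event". There is no exception for an event that becomes serious or ends treatment.

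SAP 2.8.1.1 applies the definition to the tables by system organ class and preferred term, including the part for infections, and to the tables by severity and of suspected related events. It also applies it to discontinuations: "Treatment emergent adverse events leading to permanent study drug discontinuation will be summarized by primary system organ class and preferred term". The listing has the same scope: "In addition, all the treatment emergent AEs will also be listed". The SAE table is worded differently and carries no such limit: "Number and percentage of patients with serious adverse events, regardless of study drug relationship, will be presented" by class and term.

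Protocol 9.4.1 sets the analysis that the SAP implements: "Deaths, serious adverse events, and adverse events leading to discontinuation of study drug will be summarized by primary system organ class and preferred term and" also listed. It does not mention treatment emergence. SAP section 4, on changes to the analyses specified in the protocol, reads not applicable.

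**The concern.** Severity and seriousness measure different things. Protocol 7.1 grades severity on three levels by interference with daily life, and the top one is "severe: prevents normal activities". Protocol 7.2.1 defines seriousness by consequences such as hospital admission or threat to life, and expressly covers the worsening of a pre-existing condition. An event ongoing at entry can therefore lead to admission, or to stopping canakinumab, without its grade moving. An event that is already severe has no higher grade to reach.

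Adverse events are the only outcome assessed in this study, and those that end treatment or become serious are the ones a reader of the report will look for first. If the SAP is followed as written, a patient could appear in the disposition table as stopping because of an adverse event, while the discontinuation table shows no such event and the AE listing has no line for it. A serious event could likewise appear in the SAE table with no matching line in the listing. The tables would not reconcile, and the SAP would not explain why.

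**Working it through.** The plan states no figure to reproduce, and no sample size, power or error rate is involved. The check applies the SAP's definition to each planned output and compares the result with the protocol.

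**Step 1, inputs.** The definition and listing come from SAP 2.8.1, the tables from 2.8.1.1, deaths from 2.8.2 and disposition from 2.3.1. The severity scale is in Protocol 7.1 and the protocol's analysis in 9.4.1.

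**Step 2, trace.** Take an event present at baseline whose grade does not change after the first dose. It is not treatment-emergent.

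| What happens after first dose | Class/term, infection, severity and related tables | Discontinuation table | SAE table | AE listing | Still visible in |
|---|---|---|---|---|---|
| Leads to permanent discontinuation, not serious | absent | absent | does not apply | absent | disposition table and listing, as a reason only |
| Becomes serious, treatment continues | absent | does not apply | not excluded by its wording | absent | SAE table |
| Becomes serious and ends treatment | absent | absent | not excluded by its wording | absent | SAE table; disposition reason |
| Fatal | absent | depends on action taken | not excluded by its wording | absent | deaths listing; deaths summary if within 30 days of last treatment |

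**Step 3, comparison with Protocol 9.4.1.** The protocol asks for events leading to discontinuation to be summarised by class and term and listed. The first and third rows show the SAP doing neither for these events. The protocol also asks for serious events to be listed. The second and third rows show that the only listing described does not cover them.

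**Step 4, size per patient.** The documents give no count of events ongoing at entry, so only a weight per omitted patient can be stated. Taking the planned maximum as the safety set:

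- Overall: 1/41 = 2.4 percentage points (Protocol section 4), or 1/40 = 2.5 (synopsis).
- SJIA: 12 + 21 = 33, so 1/33 = 3.0 percentage points.

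These apply to a row of a table only if the patient has no other event counted in that row.

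**The case against.** **Few such events may exist.** Protocol 7.1 counts adverse events from consent to this study. The visit schedule collects none at inclusion, where consent and the first administration both fall. Under SAP 2.3.4, conditions carried over from the parent study are medical history. Direct rollover also requires completion of the parent study with no significant safety issue. If a worsening is recorded as a new event with its own onset date, it is treatment-emergent already. This stands as an argument about size. It does not remove the gap: SAP 2.8.1 itself provides for events present at baseline, and no text tells sites to open a new record when one worsens. Protocol 7.1 has an event followed to resolution with changes assessed at each visit, and 7.2.2 has progression of an SAE reported as follow-up to the original.

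**The protocol remains the default.** The SAP Introduction follows the protocol unless otherwise specified, so the listings in 9.4.1 are not expressly withdrawn. This weakens the point on listings. It does not help the discontinuation table, where the SAP does specify otherwise.

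**A stronger reading is tempting.** A reader might infer that a baseline event that becomes serious disappears from the safety summaries altogether. The documents do not support that. The SAE table is the one adverse-event table in 2.8.1.1 without the restriction, SAP 2.8 says that all data will be used, and deaths are handled by date. At most the scope of the SAE table is unclear, because 2.8.1 sends treatment-emergent events to all summaries without saying whether others may enter.

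**The rule itself is conventional.** Defining treatment emergence by new onset or increased severity is coherent for a descriptive single-arm study. That is accepted. The fault lies in applying it to outputs that the protocol leaves unrestricted.

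**Conclusion.** The point holds in limited form. As written, the SAP drops a baseline event that ends treatment at an unchanged grade from the discontinuation table and the AE listing, and leaves it only as a disposition reason with no class or term. A baseline event that becomes serious at an unchanged grade is absent from the listing and the treatment-emergent tables, but not, on its wording, from the SAE table. Both results are narrower than Protocol 9.4.1, and SAP section 4 does not declare the difference.

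The conclusion assumes that a worsened event keeps its original record and start date; the documents do not settle this. The number of events affected is unknown and probably small. The per-patient weights are illustrations at maximum enrolment, not estimated effects. It would also be wrong to express the effect as one patient among all periodic-fever patients, because SAP 2.2.1 plans separate tables for HIDS/MKD and FMF and no pooled table.

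**What to change.** In SAP 2.8.1.1, delete the treatment-emergent qualifier from the sentence on events leading to permanent discontinuation. Add one statement, for example: *SAEs and AEs leading to permanent discontinuation are tabulated and listed if the event became serious, or study drug was stopped because of it, after the first dose in this study, whether or not the event is treatment-emergent.* This also settles the scope of the SAE table.

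The alternative is to amend SAP 2.8.1 so that a baseline event counts as treatment-emergent if, after the first dose, its grade rises, it becomes serious or it leads to permanent discontinuation. This closes the same gap for these events. It also brings them into the general treatment-emergent tables, which the first option leaves as they are.

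Either way the cost is a sentence or two and one programming condition, using the seriousness and action-taken items that Protocol 7.1 already has recorded on the AE CRF. The downside is slightly higher event counts. If the sponsor prefers to keep the present restriction, SAP section 4 should declare it as a change from Protocol 9.4.1.

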5.5.11 Early study termination

The study can be terminated at any time for any reason by Novartis. Should this be necessary, the patient should be seen as soon as possible and treated for a prematurely withdrawn patient. The investigator may be informed of additional procedures to be followed in order to ensure that adequate consideration is given to the protection of the patient's interests.

6 Visit schedule and assessments

Visits will take place at the patient's scheduled drug administration date (approximately every 4 weeks or less frequently according to investigators judgment i.e. 6, 8 or 12 weeks).

If no administration is performed within the 12 weeks of previous injection, a control visit will be performed at Week 13 +/- 7 days after the last administration in order to evaluate safety and need for the patient to continue the treatment and the study.

Table : scheduled visits and evaluations

Visits	Inclusion ⁽¹⁾	Visits for canakinumab administration ⁽⁴⁾	End of the study visit ⁽²⁾
Visit window (days)	+/- 7	+/- 7	+/- 7
Inclusion/ exclusion criteria	X		
Written informed consent	X		
Demographic data	X		
Treatment administration	X	X	X
Concomitant treatment	X ⁽³⁾	X	X
Adverse events		X	X
End of the study			X

- 1) The date of last visit of CACZ885G2301E1/CACZ885N2301/CACZ885G2306 study will be the first visit of this extension study.
- 2) The end of study is defined as premature termination or end of the study according to protocol: in the month following the availability of repaid product in France.
- 3) Corticosteroids and methotrexate only.
- 4) Visits will take place at scheduled administration date every 4, 6, 8 or 12 weeks (section 5). Dose interval may be prolonged during the study (i.e. visits every 6, 8 or 12 weeks or longer in case of adequate response at the discretion of the investigator (section 5). If no administration is performed within the 12 weeks of previous injection, a control visit will be performed at Week 13 +/- 7 days after the last administration in order to evaluate safety and need for the patient to continue the treatment and the study.

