2.1.1 General definitions

Study treatment: refers to: Ilaris = ACZ885

Study treatment start and end date: Study treatment start date is defined as the first date of study drug is administered and recorded on the Study Medication Dosing Record in CRF page. Similarly, study drug end date is defined as the last date of study drug is administered.

Study day: Study day will be calculated as (event date – study drug start date + 1 day) for events that occurred on or after study drug start date (e.g. visit, adverse events). For events prior to study drug start date (e.g., time of diagnosis), study day will be negative and calculated as (event date – study drug start date).

Baseline and post baseline: In general, a *baseline* value refers to the last measurement made prior to administration of the first dose of study treatment or the average values taken prior to administration of the first dose of study treatment. A post-baseline value refers to a measurement taken after the first dose of study treatment.

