2.7.1 Secondary endpoints

2.7.2 Statistical hypothesis, model, and method of analysis

2.7.3 Handling of missing values/censoring/discontinuations

2.8 Safety analyses

Safety measurements include, Extent of exposure and adverse events. All safety endpoints will be summarized for the safety set. All data will be used in safety analyses; however, no imputation will be carried out for missing data.

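### SAP 2.8.1 confines the AE summaries and its only general AE listing to treatment-emergent events, so some recorded non-serious AEs reach no SAP output

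*SAP*

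**What the plan says.** SAP 2.8.1 sets the window. It opens with "Adverse events starting on or after the time of the first dose of study drug" and closes "but not later than 7 days (30 days in the case of a SAE) after the date of last dose of study drug taken". AEs present at baseline that become more severe also count. Events meeting this definition go into all summaries, and the section then adds: "In addition, all the treatment emergent AEs will also be listed". The paragraph that follows gives the columns of the by-patient listing and states no wider scope. SAP 2.1.1 fixes the end of dosing by calendar date: "study drug end date is defined as the last date of study drug is administered".

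In SAP 2.8.1.1 the tables by system organ class and preferred term, by infection, by severity, by relationship and by permanent discontinuation are all labelled treatment-emergent. The SAE table does not carry that label. SAP 2.8.2 lists every death in the database, without a window.

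The protocol collects more widely. Section 7.1 defines AEs from written consent and has them sought at each visit. Section 6 adds a control visit at Week 13 ± 7 days when no dose follows within 12 weeks, "in order to evaluate safety and need for the patient to continue the treatment and the study". Section 9.4.1 states: "Adverse events will be summarized for each disease by presenting the number and percentage of patients having any adverse event". It also plans listings of deaths, SAEs and AEs leading to discontinuation. It mentions no treatment-emergent limit for any of these.

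**The concern.** Collecting serious and non-serious AEs is the study's only data objective. The analysis is descriptive, in about 40 patients, so the listing is where a reader would look at individual events. Under SAP 2.8.1 an event can be recorded, coded and monitored and still be absent from every table and listing, because both follow the same definition.

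Two things are at stake. First, visits meant to capture safety after dosing has stopped can produce non-serious AEs that the study report never shows. Second, a listing restricted to events already classified as treatment-emergent gives a reader no means of checking that classification, since the events ruled out are not visible.

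The point concerns the scope of the listing. Whether 7 days is a suitable window is a separate question.

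**Working it through.** The plan states no figure for this, so there is nothing to reproduce. The check has two parts.

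**1. Which output takes which event**

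| Event outside the treatment-emergent definition | SAP output | Protocol 9.4.1 |
|---|---|---|
| Death | Listed, no window (2.8.2) | Summarised and listed |
| SAE | Table not labelled treatment-emergent, but 2.8.1 says treatment-emergent events are what the summaries contain; no separate listing named | Summarised and listed, no limit stated |
| AE leading to discontinuation | Table labelled treatment-emergent; no separate listing named | Summarised and listed, no limit stated |
| Other non-serious AE | None | Counted under any AE; details tabulated and listed where appropriate |

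The last row is the clear gap. The two rows above it are ambiguous.

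**2. How much follow-up time is involved**

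Inputs:
- Window after last dose: 7 days for a non-serious AE, 30 days for an SAE (SAP 2.8.1).
- Last dose: date of last administration (SAP 2.1.1).
- Control visit: Week 13 ± 7 days after the last administration (protocol Section 6). 13 × 7 = 91, so Day 84 to Day 98.
- Dosing intervals of 4, 6, 8 or 12 weeks (protocol Section 6).

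Formula: uncovered days = days from last dose to visit − window.

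Non-serious AEs, patient not dosed again, control visit:
- Day 84: 84 − 7 = 77; 77/84 = 91.7%
- Day 91: 91 − 7 = 84; 84/91 = 92.3%
- Day 98: 98 − 7 = 91; 91/98 = 92.9%

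Non-serious AEs, end-of-study visit without a dose, one interval after the last one:
- 4 weeks: 28 − 7 = 21; 21/28 = 75.0%
- 8 weeks: 56 − 7 = 49; 49/56 = 87.5%
- 12 weeks: 84 − 7 = 77; 77/84 = 91.7%

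SAEs at Day 91, if the SAE output is in fact limited to the window: 91 − 30 = 61; 61/91 = 67.0%.

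These are shares of follow-up days for one pattern of dosing. If the patient is dosed again, the last-dose date moves forward, and the days between the two doses fall back inside the window.

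Before the first dose, SAP 2.8.1 also leaves out "AEs which started and ended prior to baseline" and those that began earlier and did not change in severity. The schedule in protocol Section 6 puts consent and dosing at the inclusion visit and marks no AE collection there, so this interval is normally very short.

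**The case against.** The strongest reply is that applying a treatment-emergent definition to the protocol's general term is ordinary SAP detail, and that little is really lost. Much of this stands.

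- A reader might infer that SAP 2.8 is contradicted, because it says "All data will be used in safety analyses". That sentence goes on to rule out imputation of missing data. It is about data handling and promises no listing.
- A reader might infer that protocol 9.4.1 demands a listing of every AE. It qualifies that part: other collected information is listed where appropriate. Unqualified listings are required only for deaths, SAEs and AEs leading to discontinuation.
- The SAP Introduction follows the protocol unless it specifies otherwise, and SAP Section 4 records no change to protocol-specified analyses. The protocol's SAE and discontinuation listings therefore arguably still apply. The treatment-emergent listing is the only general AE listing named in the SAP, not the only AE listing planned.
- The Week 13 visit may fall between doses. Protocol Section 5 lets patients resume after relapse and allows a dose at the final visit; in either case the gap shrinks or disappears.
- The documents do not say how many patients will stop dosing and still be followed.

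None of this creates an output for a non-serious, non-emergent AE that does not lead to discontinuation. On treatment emergence, SAP 2.8.1 does specify its own rule, so the fallback to the protocol does not clearly rescue such events.

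**Conclusion.** The point holds in a limited form. Followed as written, the SAP shows nowhere a non-serious AE that is not treatment-emergent and does not lead to discontinuation. In practice these are mainly AEs starting more than 7 days after a patient's final dose.

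For a patient never re-dosed and seen at Day 91, 84 of 91 days are uncovered, or 77 to 91 days across the visit window. This assumes that the last administration date ends dosing, that no later dose is given, and that the by-patient listing has the scope of the sentence introducing it. It would be wrong to read the 92% as a share of AEs or of patients; the documents give no event rates and no count of patients in this position.

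For SAEs and AEs leading to discontinuation the scope is ambiguous and needs a statement. Deaths are covered. The interval between consent and first dose adds little. This is a cheap improvement to a safety-only study, not a proven contradiction between the documents.

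**What to change.** In SAP 2.8.1, replace the listing sentence with: *All AEs recorded from informed consent to last study contact will be listed, with a treatment-emergent flag (yes/no).*

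Add one row per disease giving the number and percentage of patients with any recorded AE, emergent or not, so that the count in protocol 9.4.1 is met on either reading of its wording.

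State in SAP 2.8.1.1 whether the SAE and discontinuation tables are limited to treatment-emergent events, and whether the SAE and discontinuation listings in protocol 9.4.1 will be produced.

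The cost is a few SAP sentences, one listing column and one table row per disease. The downside is a somewhat longer listing. The treatment-emergent tables stay as planned, and no further data need be collected.
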